#### 7.2.12.2. Time to Medication Failure (TTMF)

Medication failure is defined in Section 4.6 of the study protocol and discussed in Section 7.1.1. TTMF will be computed as the event date (as described below) – randomization date + 1.

Kaplan-Meier methods will be used to estimate TTMF for each treatment group. Estimates of median TTMF will be provided along with 90% confidence intervals. Q1 and Q3 will also be tabulated. Comparisons between treatment groups will use the two-sided log-rank test. In addition, hazard ratio (HR) estimates with 90% CIs will be calculated from a Cox proportional hazards regression analysis that includes treatment as a factor. Censoring rules are defined as in Table 4.

**Table 4**

| Situation  | Date of Event or Censoring  | Outcome |
|---|--|----------------|
| Patient is designated a medication failure (received prohibited meds or unallowable CS burst) | Date of first dose of medication leading to medication failure designation. These dates will be identified by the sponsor based on the prior and concomitant medication eCRF form. | Event          |
| Patient withdraws from study (no medication failure)  | Censored at date of withdrawal   | Censored       |
| Patient completes the study (no medication failure)   | Censored at last study visit   | Censored       |
| Patient dies during study (no medication failure)   | Censored at the date of death  | Censored       |

Sponsor: Boston Pharmaceuticals, Inc.  
Protocol Number: BOS161721-02  
SAP Version and Date: Version 4.0, 23Apr2021

Kaplan-Meier curves of TTMF will be plotted over time.

These analyses will also be performed for the MAD Phase 1b with the exception of the statistical testing.

Time to medication failure data will be provided in a by-patient listing in the full analysis set.

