**Evaluability/Non-Responders:**

**Medication Failures:** Patients who received prohibited medications or undergo unallowable corticosteroid (CS) usage will be considered “medication failures” and will be treated as non-responders at time points on and following the first date of prohibited medication or unallowable CS usage for the primary efficacy analysis. Prohibited medications are detailed in Appendix 4 of the study protocol. Prohibited medications and unallowable CS usage will be recorded as protocol deviations in the clinical database.

A patient is considered to have unallowable CS usage if any of the following is not met:

- A maximum daily dose of 30 mg/day of oral CS will be acceptable for eligibility for the study. For patients whose only SLE treatment is steroids, their stable steroid dose must be at least 10 mg/day and no more than 30 mg/day for a minimum of 6 weeks at time of randomization on Day 0
- Topical steroids may be used, but the dose must be stable for at least 6 weeks prior to Day 0, and be maintained at a constant dose throughout the study duration until the rashes resolve. PRN topical steroids are not permitted
- Once the patient has received the first dose of study drug (Day 0), tapering of oral steroids will be highly encouraged and should be continually evaluated during the protocol-allowed tapering windows (Day 0 through Day 150) with the target of achieving a CS daily dose of < 7.5 mg and < Day 0 dose between Day 150 and Day 210
- Between Day 150 and Day 210 (i.e., within 60 days of primary endpoint assessments), oral CS doses must be held constant
- CS Burst for SLE-related Indications
  - After Day 0 (first dose of study drug), a maximum of 1 oral CS “burst” equivalent to  $\leq$  40 mg/day prednisone for increased SLE disease activity will be allowed between Day 0 and Day 120, which must be tapered down to the baseline (Day 0) CS dose or lower within 14 days of initiation of the “burst”. Any “burst” continuing after Day 120 or occurring after Day 120 is considered a protocol deviation.
  - Alternatively, a single intramuscular (IM) dose of methylprednisolone ( $< 40$  mg) is permitted during this period.
- CS Burst for Non-SLE-related Indications
  - A single treatment of oral prednisone equivalent of  $\leq$  40 mg/day for 14 days is permitted for a non-SLE indication, though it must be completed prior to Day 120. No long acting steroid injections are permitted.

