### 7.2.12. Medication Failure

#### 7.2.12.1. Proportion of Patients with Medication Failures

Patients who received prohibited medications or had unallowable CS usage as described in Section 4.6 of the study protocol will be considered “medication failures” and will be treated as non-responders at time points on and following the first date of prohibited medication or unallowable CS usage for the primary efficacy analysis and selected sensitivity and secondary efficacy analyses. The determination of medication failures and medication failure dates will be reviewed using blinded data and finalized prior to unblinding.

Sponsor: Boston Pharmaceuticals, Inc.  
Protocol Number: BOS161721-02  
SAP Version and Date: Version 4.0, 23Apr2021

The number and proportion of patients with medication failures will be summarized by study phase and treatment group in the FAS overall and by visit. A patient will be counted as a medication failure at each visit occurring on and after the date in which a patient is considered a medication failure. Statistical methods described in Section 7.1.1 will be implemented for observed data only. LOCF and missing data imputation will not be performed.

The denominator is the number of patients in FAS (overall analysis) and the number of patients with non-missing visit data (for the by visit analysis).

Statistical testing data will be omitted from MAD Phase 1b treatment group displays.

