#### 7.2.13. Duration of Longest SRI-4 Response

Duration of longest SRI-4 response will be computed for patients who have been identified as a responder at least once based on criteria defined in Section 7.1.1 utilizing LOCF methods consistent with the primary efficacy analysis. The duration of longest response will be defined as the longest period a patient meets the SRI-4 responder criteria at consecutive visits. This will be computed as the date of last consecutive SRI-4 response – date of first consecutive response + 1. If the last consecutive response is based on LOCF methods and the last consecutive response does not have a date, duration of longest SRI-4 Response will be computed as the (date of last non-missing consecutive SRI-4 response + 30) – date of first consecutive response + 1.

The duration of longest SRI-4 response will be analyzed using an analysis of variance (ANOVA) model with treatment group as the effect. The p-value for the difference between the BOS161721 and placebo group is based on the F-test.

The mean, SD, median, minimum, maximum, Q3, Q4, LS Mean estimate, its standard error and 90% CI will be tabulated by treatment group and for the difference between treatment groups (BOS161721 versus placebo).

If a patient has missed a visit between two scheduled visits with a response at both, the patient will be counted as having a response at the missed visit unless otherwise specified.

Duration of longest SRI-4 response will be displayed in the SRI response listing.

These analyses will also be performed for the MAD Phase 1b with the exception of the statistical testing.

#### 7.2.14. Time to First BILAG A Flare or >1 BILAG B Flare through Day 210

Time to first BILAG A Flare or >1 BILAG B Flare will be computed as the event date (as described below) – randomization date + 1. If a patient is designated as a medication failure prior to or on their day 210 visit, they will be considered as having a BILAG flare (event) as of the date of first dose of the medication leading to the medication failure designation due to prohibited medication or unallowable CS burst.

Time to first BILAG A Flare or >1 BILAG B Flare will be analyzed with Kaplan-Meier methods described for TTMF and censoring as described in Table 5. Kaplan-Meier curves will be plotted over time.

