**Table 5**

| Situation   | Date of Event or Censoring   | Outcome |
|--|---|----------------|
| Patient has a BILAG A Flare or >1 BILAG B Flare (Noted as BILAG 1A/2B Flare) prior to or on their Day 210 visit                  | Date of first BILAG 1A/2B Flare   | Event          |
| Patient is designated a medication failure (received prohibited meds or unallowable CS burst) prior to or on their Day 210 visit | Date of first dose of medication leading to medication failure designation. These dates will be obtained from date of the medication failure identified by the sponsor based on the prior and concomitant medication eCRF form. | Event          |
| Patient withdraws from study (no BILAG 1A/2B Flare, no medication failure) prior to or on their Day 210 visit                    | Censored at date of last non-missing BILAG flare assessment (prior to or on withdrawal) through Day 210   | Censored       |
| Patient completes the study (no BILAG 1A/2B Flare, no medication failure)  | Censored at date of last non-missing BILAG flare assessment through Day 210   | Censored       |
| Patient dies during study (no BILAG 1A/2B Flare, no medication failure) prior to or on their Day 210 visit                       | Censored at the day of death  | Censored       |

An event will be counted once in a patient who is a medication failure and also experiences a BILAG flare. Date of event will be the date of the earlier of the two reasons.

These analyses will also be performed for the MAD Phase 1b with the exception of the statistical testing.

Time to first BILAG A Flare or >1 BILAG B Flare data will be provided in a by-patient listing in the full analysis set.

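### Table 4, Section 7.2.14 and Table 5 date a medication failure at the first dose of the drug, while Sections 7.1.1, 7.2.1 and 7.2.12.1 date it at the first unallowable use; one rule is needed

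*SAP*

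**What the plan says.** Section 7.1.1 treats a medication failure as a non-responder "on and following the first date of prohibited medication or unallowable CS usage". Section 7.2.1 applies the same start date to the by-visit responses. Section 7.2.12.1 repeats it for the proportion of failures: "at time points on and following the first date of prohibited medication or unallowable CS usage".

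The time-to-event sections use a different anchor. Table 4, for time to medication failure (TTMF), gives the event date as "Date of first dose of medication leading to medication failure designation", to be identified by the sponsor from the medication eCRF form. Section 7.2.14 counts a medication failure as a flare "as of the date of first dose of the medication leading to the medication failure designation due to prohibited medication or unallowable CS burst". Table 5 repeats the first-dose wording and adds: "These dates will be obtained from date of the medication failure identified by the sponsor".

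Section 7.1.1 also describes steroid use that can begin within the limits and leave them later:
- One oral burst for SLE is allowed from Day 0 to Day 120, subject to a limit on its length: "which must be tapered down to the baseline (Day 0) CS dose or lower within 14 days of initiation".
- A burst for another indication ("A single treatment of oral prednisone equivalent of" at most 40 mg/day) is allowed for 14 days and must be finished before Day 120.
- Oral doses must be held constant between Day 150 and Day 210, and any other increase over baseline through Day 210 makes the patient a failure.

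**The concern.** A course that starts inside the limits and breaches them later has two candidate failure dates, and the SAP has no sentence that chooses between them. Table 5 equates the first-dose date with the sponsor's failure date. If that one date is used throughout, it also reaches the by-visit SRI analyses (7.2.1 to 7.2.3), percent steroid reduction (7.2.4.3), the carry-forward and exclusion approaches of 7.2.6.2 and the sections that reuse them, the by-visit failure proportion (7.2.12.1) and the longest response (7.2.13). If two dates are kept, a patient can have an event in TTMF before being a failure in the by-visit tables.

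First-dose dating also makes the event depend on later conduct. A patient who withdraws during a burst that is still within limits is censored in TTMF. One who stays and overruns has an event placed back at the burst's first day.

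**Working it through.** The SAP states no figure for this point: it gives no failure rate and no expected number of overruns. The check is therefore date arithmetic, followed by a small simulation under assumed rates.

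**Inputs**
- Time = event date − randomization date + 1 (Sections 7.2.12.2 and 7.2.14).
- Randomization on Day 0, a 14-day limit on a burst, and the Day 120 limit (Section 7.1.1).

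**Overrunning SLE burst that starts on Day s**
- First-dose date: s.
- First unallowable day: about s + 14, or Day 121 if that comes earlier, since a burst may not continue after Day 120.
- Shift: min(14, 121 − s) days. How the fourteenth day is counted could move this by a day.

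| Start | First-dose date | First unallowable day | TTMF, first dose | TTMF, first unallowable | Shift |
|---|---|---|---|---|---|
| Day 60 | 60 | 74 | 60 − 0 + 1 = 61 | 74 − 0 + 1 = 75 | 14 |
| Day 106 | 106 | 120 | 107 | 121 | 14 |
| Day 119 | 119 | 121 | 120 | 122 | 2 |

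For the Day 60 start, the Day 60 visit is a failure visit under first-dose dating and not under the other rule. For a Day 40 start, the gap (Days 40 to 53) contains no scheduled visit, so by-visit status is the same either way.

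**Changed background steroid**
- Suppose the dose is changed on Day 170, inside the window in which it must be constant. The Section 7.1.1 date gives 170 − 0 + 1 = 171 days.
- Read literally, the first dose of that drug is at or before randomization. Section 7.1.1 requires patients whose only SLE treatment is steroids to have been stable for at least 6 weeks (42 days). Their literal time is then −42 + 1 = −41 or lower, which is not a usable event time.
- The event rows of Tables 4 and 5 name only prohibited medication and an unallowable burst, so this kind of failure has no dating rule of its own.

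**Day 210 primary endpoint**
- A burst that starts as permitted starts by Day 120 and becomes unallowable by about Day 121. Both dates precede Day 210, so the patient is a non-responder either way.
- A background dose change that counts as a failure happens by Day 210, and the first-dose date is earlier still. The status is again the same.

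**Log-rank test, under assumed rates**
- Assumptions: 64:32 patients (96 evaluable at 2:1), placebo failure by Day 120 of 20% or 40%, hazard ratio 0.5, and 25%, 50% or 100% of failures being overruns dated 14 days apart; 300 simulated trials per setting.

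| Placebo failure | Share overrunning | Mean absolute change in Z | Largest |
|---|---|---|---|
| 20% | 25% | 0.009 | 0.050 |
| 20% | 50% | 0.010 | 0.050 |
| 20% | 100% | 0 | 0 |
| 40% | 25% | 0.020 | 0.115 |
| 40% | 50% | 0.023 | 0.131 |
| 40% | 100% | 0 | 0 |

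The test depends on the order of events, so a common shift of 14 days leaves it unchanged. The simulation has no withdrawals and no background-steroid failures, and it applies the full 14 days even to late bursts.

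**The case against.** The best defence reads the burst as a unit. Section 7.1.1 exempts only a burst that is tapered in time and disallows any other increase. An untapered burst could then be said never to have met the exemption, so that its first dose and its first unallowable use fall on the same day. Tables 4 and 5 speak of an unallowable burst, which fits that reading. It is possible, but the SAP does not state it, and it does not help with a changed background steroid.

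For the background steroid, it can be said that a stable dose taken before randomization did not lead to the designation, and that the sponsor fixes dates by blinded review rather than by taking the earliest record. A sensible reviewer would indeed avoid a negative time. The SAP still gives that reviewer no rule to apply.

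For time to flare, an SLE burst is given for increased disease activity, so its start may lie nearer the flare than the day the taper limit lapses. This stands: first-dose dating may be deliberate for that endpoint.

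Two stronger readings are tempting and should be resisted. A reader might infer that every overrun is dated at least 14 days early. About 14 days is the maximum for a burst, and the Day 120 limit shortens it. A reader might also infer that about 47% of overrunning patients (14/30) have a visit that changes to non-response. That figure assumes burst starts spread evenly over a 30-day visit cycle and a first-dose date that overrides Section 7.2.1, which the SAP does not say. Even then, the response changes only for patients who would otherwise have responded at that visit.

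**Conclusion.** The inconsistency is real and should be corrected, with limited consequences. Two rules in the SAP give different failure dates for use that starts within limits and breaches them later. The difference is up to about 14 days per overrunning burst. For a background steroid, the first-dose wording yields no usable date.

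Kaplan-Meier curves and medians for TTMF and time to flare can move accordingly. By-visit status moves only if the sponsor's single date feeds those derivations. A reader might infer that the main efficacy conclusion is at risk; it is not, because Day 210 SRI-4 status is the same under either date. The log-rank effect is likely negligible, which rests on assumed failure rates and on a simulation without withdrawals. For time to flare, the SAP does not establish that the earlier date is wrong. The number of affected patients is unknown and could be zero.

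This rests on the SAP alone. Protocol Section 4.6, to which the SAP refers for the definition of medication failure, was not examined.

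**What to change.** Reconcile the sections with one failure-date rule before unblinding:
- In Table 4, replace first-dose dating with the date that Sections 7.1.1 and 7.2.12.1 already state, the first day on which use was prohibited or unallowable.
- Widen the event rows of Tables 4 and 5 from prohibited medication or a burst to all unallowable steroid use, so that background dose changes are covered.
- Use that date in every derivation that refers to the medication failure date.
- For time to flare (Section 7.2.14 and Table 5), use the same date or state explicitly that burst start is intended.

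The cost is SAP wording and a sponsor's blinded date list built to that definition. No steroid rule changes; only the dating of the event does.

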#### 7.2.13. Duration of Longest SRI-4 Response

Duration of longest SRI-4 response will be computed for patients who have been identified as a responder at least once based on criteria defined in Section 7.1.1 utilizing LOCF methods consistent with the primary efficacy analysis. The duration of longest response will be defined as the longest period a patient meets the SRI-4 responder criteria at consecutive visits. This will be computed as the date of last consecutive SRI-4 response – date of first consecutive response + 1. If the last consecutive response is based on LOCF methods and the last consecutive response does not have a date, duration of longest SRI-4 Response will be computed as the (date of last non-missing consecutive SRI-4 response + 30) – date of first consecutive response + 1.

The duration of longest SRI-4 response will be analyzed using an analysis of variance (ANOVA) model with treatment group as the effect. The p-value for the difference between the BOS161721 and placebo group is based on the F-test.

The mean, SD, median, minimum, maximum, Q3, Q4, LS Mean estimate, its standard error and 90% CI will be tabulated by treatment group and for the difference between treatment groups (BOS161721 versus placebo).

If a patient has missed a visit between two scheduled visits with a response at both, the patient will be counted as having a response at the missed visit unless otherwise specified.

Duration of longest SRI-4 response will be displayed in the SRI response listing.

These analyses will also be performed for the MAD Phase 1b with the exception of the statistical testing.

#### 7.2.14. Time to First BILAG A Flare or >1 BILAG B Flare through Day 210

Time to first BILAG A Flare or >1 BILAG B Flare will be computed as the event date (as described below) – randomization date + 1. If a patient is designated as a medication failure prior to or on their day 210 visit, they will be considered as having a BILAG flare (event) as of the date of first dose of the medication leading to the medication failure designation due to prohibited medication or unallowable CS burst.

Time to first BILAG A Flare or >1 BILAG B Flare will be analyzed with Kaplan-Meier methods described for TTMF and censoring as described in Table 5. Kaplan-Meier curves will be plotted over time.

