## 2.2. Proof of Concept (POC) Phase 2 Study

| Objectives       | Endpoints  |
|------------------|--|
| Primary   | 
Primary Efficacy Endpoint
 
 
The proportion of patients with a SRI-4 response at Day 210
 
   |
| Secondary | 
Secondary Efficacy Endpoints
 
 
The proportion of patients with:             
 
- SRI-4 response at each visit
 
- SRI-5 and SRI-6 response at each visit
 
- a sustained reduction of oral corticosteroid (CS) (<math>\leq 7.5</math> mg/day and <math><</math> Day 0 dose) between Day 150 and Day 210
 
- new or recurrent BILAG flares (<math>\geq 1</math> qualifying BILAG A or <math>> 1</math> qualifying BILAG B) through Day 210
 
- PGA worsening
 
- a BICLA response
 
- a CLASI response
 
- medication failures
 
 
 
Change and percentage change from baseline at each visit in:             
 
- CLASI
 
- PGA
 
- Total number of swollen joints, tender joints, and active joints (swelling and tenderness in the same joint) in the ACR-28 joint count
 
- SLEDAI-2K
 
- SLICC/ACR damage index
 
 
 
TTMF
 
Group mean percent reduction in corticosteroid administration from baseline Day 0 dose through Day 210 in patients receiving <math>\geq 7.5</math> mg/day prednisone equivalent at Day 0
 
 |

Sponsor: Boston Pharmaceuticals, Inc.  
Protocol Number: BOS161721-02  
SAP Version and Date: Version 4.0, 23Apr2021

| Objectives | Endpoints  |
|------------|--|
|            | 

• Duration of longest SRI-4 response

• Time to first BILAG flare (<math>\geq 1</math> new or recurrent BILAG A or <math>> 1</math> new or recurrent BILAG B) relative to baseline through Day 210

   |

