### 3.3. Sample Size Considerations

Sample size in the Phase 1b part of the study is based on operational consideration.

The sample size in the Phase 2 POC study is based on the primary endpoint, SRI-4 Response at Day 210. Based on efficacy data from a recently completed study with Ustekinumabiii, where the primary endpoint was also SRI-4, the sample size in the phase 2 part of the BOS161721-02 study is set at 96 evaluable patients. In the Ustekinumab study of 102 patients, a statistically significant difference in SRI-4 response was shown in favor of Ustekinumab (62% of Ustekinumab treated patients achieved SRI-4 response vs. 33% in patients receiving placebo). The Ustekinumab phase 2 study is an appropriate comparator to BOS161721-02 because both studies share the same primary endpoint of SRI-4 response and BOS161721 and Ustekinumab have overlapping mechanisms of action (T follicular helper and Th17 cell biology).

Sponsor: Boston Pharmaceuticals, Inc.  
Protocol Number: BOS161721-02  
SAP Version and Date: Version 4.0, 23Apr2021

Approximately 110 additional patients will be randomized in a 2:1 ratio to BOS161721 versus placebo to achieve approximately 96 evaluable patients in the FAS of the phase 2 portion. This assumes 14 patients will discontinue prior to having received treatment or having completed a post-baseline efficacy measure. Enrollment and randomization will be monitored in a blinded fashion and may be increased if needed to ensure at least 96 evaluable patients are randomized into the FAS (see Section 6.1).

A total of 96 evaluable patients randomized provides 80% power to detect a treatment difference of 29% in SRI-4 response rates at Day 210, based on a targeted 2-sided significance level of 10% and using a 2-sided Pearson's chi-squared test. This assumes a response rate of 62% for BOS161721 and 33% for placebo.

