## 4. DATA ANALYSIS CONSIDERATIONS

All analyses will be conducted based on SAS 9.3 or higher.

All data in the database will be presented in by-patient data listings.

Unless otherwise stated, all listings will be sorted by study phase, treatment group, patient number, and assessment date (and time, if available). If assessment date is missing, chronological visit will be used for sorting.

Unless stated otherwise, continuous data will be summarized by treatment group based on number of patients (n), mean, median, standard deviation (SD), 25th percentile/first quartile (Q1), 75th percentile/third quartile (Q3), minimum value, and maximum value.

The geometric % coefficient of variation (CV) is calculated as  $100 * \sqrt{\exp(SD\log^2) - 1}$  where SDlog is the SD of log-transformed values.

Unless stated otherwise, categorical data will be summarized by treatment group using n and percentage based on the number of non-missing values.

- The number of missing values will be presented as a separate category with no percentage, but only if one or more patients are missing data.
- Counts of zero will be presented without percentages.

Sponsor: Boston Pharmaceuticals, Inc.  
Protocol Number: BOS161721-02  
SAP Version and Date: Version 4.0, 23Apr2021

Statistics will be presented in the summary tables based on the following:

- Minimum and maximum: same number of significant digits as the raw value
- Mean, median, Q1, and Q3: one additional decimal place to that reported for minimum and maximum
- SD: two additional decimal places than presented for the minimum and maximum
- Percentages: reported to one decimal place with the exception of 100% which will be displayed without decimals.
- P-values will be reported to four decimal places. If the value is below 0.0001 it will be noted as < 0.0001; if the value above 0.9999 it will be noted as > 0.9999.

Unless otherwise noted, statistical inference will be based on a 10% significance level (i.e. 90% confidence intervals will be produced).

Statistical testing will be performed on data from the Phase 2 study.

Numbering for data displays will be based on ICH E3.

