## 5.8. Missing Data

Missing data imputation for the efficacy endpoints are discussed in the corresponding efficacy sections. AE, concomitant medication, and corticosteroid date imputations are described in Section 5.5. Missing data and other analysis conventions for noncompartmental analysis of pharmacokinetics will follow standard imputation methods, as described in a separate Clinical Pharmacology SAP. Otherwise, missing data will not be imputed.

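### Duration of longest SRI-4 response is tested only among patients who responded at least once, so its p-value and 90% CI do not estimate a randomised treatment effect

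*SAP*

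**What the plan says.** SAP section 2.2 lists this duration among the secondary efficacy endpoints of the Phase 2 part. Section 7.2.13 (version 4.0) sets the population: "Duration of longest SRI-4 response will be computed for patients who have been identified as a responder at least once". Duration runs from the first to the last of a series of consecutive response visits, plus one day, and the longest such series counts. The model follows: "The duration of longest SRI-4 response will be analyzed using an analysis of variance (ANOVA) model with treatment group as the effect". On the test: "The p-value for the difference between the BOS161721 and placebo group is based on the F-test". LS means and 90% CIs are tabulated for each arm and for the difference. Section 4 sets the general rule that "statistical inference will be based on a 10% significance level".

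No duration is assigned to a patient who never responds. Section 5.8 refers efficacy imputation to the efficacy sections and then closes the matter: "Otherwise, missing data will not be imputed". Neither section 7.2.13 nor the list of changes in section 11 contains a version that includes all FAS patients, or a caveat on the comparison.

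**The concern.** Whether a patient ever responds is settled after randomisation, and it is what the drug is meant to influence. If the drug works, the active responders are a mixture: patients who would also have responded on placebo, and patients who respond only because of the drug. The placebo counterparts of the second group never respond and are absent. The two sets of responders are therefore not comparable by randomisation, and the difference in their mean durations mixes any effect on duration with a change in who is counted.

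Two misreadings are possible. A drug that produces many more responses, each as durable as those on placebo, would show no difference. A drug whose added responses are late or brief could show a difference in favour of placebo, although its patients spend more time in response overall. Either result would be reported with a p-value and a CI.

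**Working it through.** **Sample size.** The SAP states no size or power for this endpoint. Section 3.3 gives 96 evaluable patients for the primary endpoint (62% against 33%, 2:1, two-sided 10%, 80% power). The two-proportion formula with continuity correction returns 32 placebo + 64 active = 96, so 64:32 is used below.

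**Who enters the ANOVA.** The SAP gives no ever-response rates. The Day 210 rates serve as an assumption; true ever-response rates can only be as high or higher, because a Day 210 responder is an ever-responder.
- Active: 0.62 × 64 = 39.7, about 40 enter and 38% are left out.
- Placebo: 0.33 × 32 = 10.6, about 11 enter and 67% are left out.

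**Expected differences.** Assume that a share r0 of each arm responds regardless of treatment, with mean duration m0 in both arms. Assume that the drug adds responders up to a share r1, with mean duration m+. Then:
- Responder-only difference = [(r1 - r0) / r1] × (m+ - m0). At 62% and 33% the factor is 0.29 / 0.62 = 0.468.
- All-patient difference, with 0 days for never-responders = (r1 - r0) × m+, which is 0.29 × m+.

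The first has the sign of m+ - m0, whatever the gain in response rate. The second is positive whenever the drug adds responders.

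**Scenarios.** All durations are assumptions. With seven monthly visits from Day 30 to Day 210, durations fall on a 30-day grid from 1 to 181 days. A range such as 61-181 means grid values with equal weight. The first two rows and the 50% / 75% row with means 103 and 28 use unequal weights. Each row rests on 3000 or 4000 simulated trials of 64:32, tested at two-sided 10%.

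| r0 / r1 | m0 (range) | m+ (range) | Responder-only: formula; simulated | Significant for placebo | All patients: formula; simulated |
|---|---|---|---|---|---|
| 33% / 62% | 103 | 103 | 0; about 0 | 5% | +29.9; +30 |
| 33% / 62% | 103 | 28 | -35.1; -35 | 50% | +8.1; +8 |
| 33% / 62% | 121 (61-181) | 121 (61-181) | 0; about 0 | 5% | +35.1; +36 |
| 33% / 62% | 121 (61-181) | 91 (61-121) | -14.0; -14 | 28% | +26.4; not given |
| 33% / 62% | 121 (61-181) | 91 (1-181) | -14.0; -14 | 15% | +26.4; not given |
| 33% / 62% | 121 (61-181) | 61 (1-121) | -28.1; -28 | 47% | +17.7; +18 |
| 33% / 62% | 91 (1-181) | 31 (1-61) | -28.1; -28 | 42% | +9.0; not given |
| 33% / 62% | 121 (61-181) | 31 (1-61) | -42.1; -42 | 71% | +9.0; +9 |
| 50% / 75% | 103 | 28 | -25.0; -25 | 40% | +7.0; +7 |
| 50% / 75% | 121 (61-181) | 31 (1-61) | -30.0; -30 | 61% | +7.8; +7 |

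In the two equal-duration rows the responder-only test is also significant for the drug in about 5% of trials, which is chance alone. In the rows with 103 and 28 days it is significant for the drug in 0.1% or fewer.

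**No drug effect.** With 33% ever-response in both arms and the same durations, the responder-only test rejects in about 10% of trials, its nominal level.

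**The case against.** The strongest reply is that duration of response is by custom a responder quantity and answers a sensible question: how long does a response last once it is achieved? As a description this stands, and the fix keeps it. It does not justify a between-arm p-value and CI. The plan's own time-to-event endpoints, in Tables 4 and 5, specify an outcome for patients without the event. This endpoint drops them.

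The consequence is also limited, and that stands. This is one of many secondary endpoints in a proof-of-concept study with no multiplicity adjustment. The superiority conclusion rests on SRI-4 at Day 210. Section 7.2.1 compares SRI-4 response at every nominal visit in the FAS, so a reader can see whether and when more patients respond.

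It is fair, too, that an all-patient duration is a different quantity. It is driven largely by response rate and overlaps with the primary endpoint, so the plan should say what it measures.

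A reader might infer that the test will favour placebo whenever the drug creates more responders. The documents do not support this. More responders alone give a difference of about zero; a reversal also needs the added responses to be shorter, and the SAP gives no durations. The 71% belongs to the scenario in which the two duration ranges share only the value 61 days, and it is the top of a range. Nor is the type I error inflated when the drug affects neither response nor duration. The fault lies in what is being estimated.

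**Conclusion.** The point holds as a flaw in the stated analysis of a secondary endpoint. The F-test and 90% CI in section 7.2.13 compare subsets chosen by a post-randomisation outcome and cannot be read as a treatment effect on duration.

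Its size rests on two sets of assumptions that the SAP does not supply: ever-response rates (62% and 33% borrowed from Day 210, or 50% and 75%) and response durations. At the borrowed rates, added responses as long as the others give a responder-only difference near 0 days, against about +30 to +36 days over all patients. Across both sets of rates, shorter added responses give about -14 to -42 days, significant for placebo in about 15% to 71% of trials. Where the all-patient difference was simulated in those cases, it still favours the drug, by about +7 to +18 days. Higher ever-response rates leave out fewer patients but keep the comparison conditional on response. The primary analysis is untouched.

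**What to change.** For the between-arm test in section 7.2.13, include every FAS patient with at least one evaluable post-baseline SRI-4 assessment, counting those who are non-responders by rule, and assign 0 days to patients who never respond. Defining the set over all visits avoids losing a patient who responded earlier but is not evaluable at Day 210. Compare arms by a Wilcoxon rank-sum test, or by the planned ANOVA with a permutation or bootstrap CI. State that the endpoint then measures time in response over all patients. Keep the responder-only duration as a descriptive summary, without a p-value or between-arm CI.

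The cost is a change of wording and one recoded variable; no new data are needed, and it can be settled before unblinding. The spike at zero is the reason to prefer ranks. In the scenario with m0 = 121 and m+ = 31 days at 33% / 62%, the all-patient ANOVA was significant for the drug in 18% of trials and the Wilcoxon test in 53%.
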